3.9 DATA ANALYSIS

Baseline demographic and psychosocial factors will be summarized for each randomized group for ITT and Evaluable Populations. For continuous variables, such as age and PAP usage, the mean, standard deviation, median, and range will be presented. For categorical variables, such as gender, the number and proportion of participants in each category will be presented. Baseline demographics and psychosocial factors for the control and intervention groups will be compared with t-tests and Fisher's exact tests, as appropriate.

The primary analysis compares mean PAP usage at 90 days in the control and intervention groups using a two-way ANOVA on the ITT population. Randomization group and myAir usage (Yes/No) will be included as factors in the model. The interaction of the two factors will be considered, but will only be retained in the model if it is significant at the 5% level. Missing usage hours during a day will be imputed as 0 usage. A secondary analysis of mean PAP usage will be conducted using the Evaluable Population. A sensitivity analysis of the missing data assumption will be conducted by considering missing data as missing. In this analysis, participants with no usage data will be assumed to have a mean usage of 0 hours; other participants' mean usage will be calculated as the mean usage across nights for which there is data.

A subgroup analysis of the primary endpoint will be generated for patients who are identified as strugglers. A struggler is defined as a patient who uses their device for less than or equal to 3.5 hours/night during the first 3 days of usage. Mean PAP usage at 90 days will be compared in the control and intervention groups using a two-way ANOVA on the struggler population as described above. Descriptive statistics will also be presented for mean PAP usage, comparing strugglers and non-strugglers in control and intervention groups.

Adherence will be calculated for the ITT population from daily usage data using the Medicare definition for adherence (a patient is adherent if they use the device for more than 4 hours per night for 70% of the nights during the first 90 days of usage). Percent adherence will be compared between control and intervention groups using a logistic regression model on the ITT population. Randomization group, myAir usage, and the interaction of these two factors will be included in the model. Missing usage hours during a day will be imputed as 0 usage.

Mean change in ESS and FOSQ questionnaire scales will be compared between control and intervention groups using a mixed-effects linear model on the ITT population and a two-sample t-test on the Evaluable population. In the mixed-effects model, the response variable will be the mean questionnaire score and the model will include randomized group, visit, and a randomized group by visit interaction as fixed effects and subject as a random effect.

Baseline perceived disease severity, claustrophobia, coping skills, and health literacy will be tested as moderators of the intervention's effectiveness. Baseline scores will be regressed on the primary outcome (usage), and then in a mixed-effects model, the response variable will be usage and the model will include baseline score, randomized group, and a randomized group by baseline score interaction as fixed effects and subject as a random effect.

An exploratory analysis will examine how engagement with the study is associated with PAP usage. Engagement will be measured as app usage (number of touches). A linear regression model with PAP usage as the dependent variable and engagement as the independent variable will be fit to all ITT subjects (engagement is zero for all control subjects). An exploratory analysis will also test whether the intervention has a direct or indirect effect on the following psychosocial factors: the pros and cons of change, self-efficacy, and social support. Finally, an exploratory analysis will test whether nomination of, and the extent of engagement with, a social support person moderates the intervention effectiveness.

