3.6 SAMPLE SIZE

N= 300

A minimum total sample size of 270 patients, with 2:1 randomization (180 in Control group, 90 in Test group) is required to yield an 80% probability of detecting a difference of 0.8 hours in mean usage (160% of the minimally clinically significant difference) when the standard deviation is 2.5 and 2.0 in the Control and Test groups, respectively. The required sample size was calculated in the Two Sample T-Tests Assuming Unequal Variances Procedure using NCSS Power Analysis Statistical Software, Version 16 (PASS 16¹⁴) based on a one-sided, two sample t-test, using a significance level of 0.025.

Assuming a potential 10% drop-out rate due to study withdrawal or lost-to-follow-up, the final sample size will be 300 patients (270/0.9), equating to 200 in the Control group and 100 in the Test Group. The 2:1 randomization ratio was chosen because it is more cost-effective to enroll subjects in the control group.

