4.2 INITIAL (ENROLLMENT) CONTACT

1. Provide patient with access to informed consent document.
2. When consent has been obtained, collect device information (device ECN, device settings, mask type), demographic, and baseline data into the electronic data capture (EDC) system.
3. Randomize participant in EDC.
 - a. Participants randomized to the Control group (Group A) will complete a set of baseline questionnaires.
 - b. Participants randomized to the Treatment group (Group B) will complete a set of baseline questionnaires and provided with instructions to download Restful to their smartphone.
 - c. Monitor both groups' PAP device usage per your standard of care.

[figure not shown]
4.3 90-DAY STUDY CONTACT

1. Both Group A and Group B will be asked to complete a set of end of study questionnaires. Restful will be 'turned off' for Group B participants.
2. Continue to monitor participants' PAP device usage per your standard of care.
3. Distribute compensation for study participation.

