4.4 REPORT OF DEVICE USAGE DATA

1. A report of PAP usage data (including average hours used per day, leak, pressure, and AHI) will be generated by the ResMed Data Analytics group at 90 days and 180 days and provided to the statistician for analysis.
2. A user-level analytics report of myAir engagement (including participants who registered for myAir and number of times they engaged with the app during the study) will be generated by the ResMed Data Analytics group at 90 days and 180 days and provided to the statistician for analysis.
3. A user-level analytics report of Restful engagement (including participants who registered for Restful and number of times they engaged with the app during the study) will be generated by Wellth at 90 days and 180 days and provided to the statistician for analysis.

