5.3 MYAIR

In addition to AirView, a patient-focused version of the data is available through the myAir app. The myAir app can be accessed via the participant's smartphone or computer and allows the participant to monitor their own treatment data. myAir also provides tips to the participant on things like coping with therapy, managing mask leaks, and adjusting comfort settings. These tips are personalized based on each individual's data. The myAir app is not mandatory in this trial, but participants' usage of myAir will be documented in both Group A and Group B.

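### The primary usage and adherence models adjust for myAir use, which is optional, undefined and not fixed at baseline, and no group-only test is planned

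*Combined protocol and SAP*

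**What the plan says.** Section 3.9 specifies a two-way ANOVA on the ITT population for mean PAP usage at 90 days: "Randomization group and myAir usage (Yes/No) will be included as factors in the model". The group-by-myAir interaction "will only be retained in the model if it is significant at the 5% level". The struggler subgroup is compared "using a two-way ANOVA on the struggler population as described above". For Medicare-defined adherence, the first-listed secondary endpoint, the logistic model goes further: "Randomization group, myAir usage, and the interaction of these two factors will be included in the model".

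On myAir itself:

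- Section 5.3: "The myAir app is not mandatory in this trial"; its use is to be documented in both groups.
- Section 4.4: a report at 90 and 180 days covers "participants who registered for myAir and number of times they engaged with the app during the study".
- Section 4.2: at enrolment, staff "collect device information (device ECN, device settings, mask type), demographic, and baseline data"; no myAir item is named.

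Section 3.6 sizes the trial on a comparison without myAir, "based on a one-sided, two sample t-test, using a significance level of 0.025", under unequal variances.

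**The concern.** Random allocation protects a comparison by assigned group, or one adjusted for variables fixed before assignment. As described, myAir use looks like a behaviour recorded during follow-up. Restful is meant to raise engagement with therapy. myAir is a second engagement app, so Restful could plausibly draw people to it or displace it. In either case, holding myAir use constant removes part of the randomised effect or adds something that is not part of it. myAir need not itself affect usage for this to happen. It is enough that more diligent participants both use the app and use their device more.

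This is the only model named for the primary comparison, so a real effect could be missed or a false one reported. A second issue is that, once the interaction is in the model, the plan does not say which group contrast is tested. The reported effect could be that in one myAir stratum or an average over strata, and the choice could be made after seeing the data.

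**Working it through.** **1. The plan's own figure.** Inputs from 3.6: difference 0.8 h, SD 2.5 (control) and 2.0 (test), 180/90, one-sided 0.025.

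SE = √(2.5²/180 + 2.0²/90) = √(0.0347 + 0.0444) = 0.281, and 0.8/0.281 = 2.84.

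The unequal-variance t-test has 80.8% power, and 270/0.9 = 300. The stated size reproduces, for a group-only test.

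**2. What the adjusted model estimates.** Write expected usage as a + τ·group + b·myAir, with uptake p1 (intervention) and p0 (control). Averaging over myAir within each arm:

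total randomised effect = τ + b(p1 - p0), so τ = total effect - b(p1 - p0).

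The ANOVA tests τ. Its bias is -b(p1 - p0), which is zero when uptake is equal and there is no interaction.

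**3. Size of the bias.** b and uptake are assumptions. Taking b = 0.5 to 2.0 h:

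- 10-point uptake gap: 0.05 to 0.20 h
- 20-point uptake gap: 0.10 to 0.40 h

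Together this is 0.05/0.8 = 6% to 0.40/0.8 = 50% of the target difference, in either direction.

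**4. Effect on the test.** Simulated at 180/90, total SD held at 2.5/2.0, control uptake 50%, one-sided 0.025, using the planned pooled-variance ANOVA without interaction. The 20-point rows give the range over repeated runs; the main run used 3,000 trials per scenario.

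| Scenario | b = 0.5 | b = 1.0 | b = 1.5 | b = 2.0 |
|---|---|---|---|---|
| Type I error, uptake 20 points lower with Restful | 0.033–0.045 | 0.078–0.084 | 0.147–0.17 | 0.26–0.282 |
| Type I error, 10 points lower | 0.023 | 0.038 | 0.051 | 0.086 |
| Power for 0.8 h, equal uptake | 76% | 78% | 81% | 84% |
| Power, 10 points higher | 69% | 67% | 62% | 59% |
| Power, 20 points higher | 62–64% | 51–52% | 38–40% | 27–28% |

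At equal uptake the ANOVA's type I error is 0.013 to 0.018. The group-only unequal-variance test has about 81% power throughout. For b = 1.5 and a true 0.8 h, the mean adjusted estimate was 0.50 h with uptake 20 points higher and 1.10 h with it 20 points lower, as the formula gives (0.8 ∓ 1.5 × 0.2).

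**5. Interaction in the adherence model.** Assumed 45% vs 62% adherent, 200/100, equal uptake, no true interaction, 20,000 trials. Power at 30/50/70% myAir use:

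- reference-cell coding (effect in one stratum): 64/50/32%
- equal-weight contrast over strata: 72/80/72%
- group alone: 79%

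**6. Interaction pre-test in the ANOVA.** Null trials at 200/100, SD 2.4, assumed myAir effect 1 h. Two-sided type I error at 30/50/70% use is 5.6/6.7/6.8% under reference-cell coding and 5.1 to 5.2% under the equal-weight contrast.

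**The case against.** The strongest reply is that post-randomisation status is inferred. Section 3.9 gives no time point, a report produced at 90 days can contain earlier registration dates, and the enrolment list in 4.2 ends with open-ended baseline data. The questionnaire outline in Appendix A is not available here, so a baseline myAir item cannot be excluded. This stands as a limit. But section 3.9 points to no such item, and without a definition, use during follow-up remains a permitted reading and the likeliest one.

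No document says Restful promotes or displaces myAir, so every figure for harm is conditional. That also stands. So does the point that a 10-point gap does much less damage than a 20-point one, although power is then still only 59 to 69%.

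Part of the shortfall against 81% comes from pooling variances under 2:1 allocation, about 4 to 5 points at small b. Comparing the ANOVA with itself removes this: from equal uptake to a 20-point excess, power falls from 76% to about 63% at b = 0.5 and from 84% to about 28% at b = 2.0.

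The moderator models in 3.9 relate usage to group without myAir. They include a baseline score and its interaction with group, so they do not supply an overall test. Group means of usage are planned only descriptively.

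Finally, the interaction problem is material only under reference-cell coding, which the plan does not state. Alone, that would be a request for clarification.

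**Conclusion.** The concern holds and should be fixed before analysis. The primary, struggler and adherence models all condition on an undefined, optional behaviour, and no planned test of usage or adherence compares the randomised groups alone. The estimate need not equal the randomised effect. Whether it will differ, and in which direction, depends on myAir uptake by arm and on the usage gap between users and non-users, neither of which the documents give. Over the assumed range (b of 0.5 to 2.0 h, uptake gaps of 10 to 20 points) the bias is 0.05 to 0.40 h, enough at the upper end to invalidate the test. It vanishes if uptake is equal and there is no interaction. The unstated contrast is a lesser fault. The sample size calculation is not in error.

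**What to change.** In section 3.9:

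1. Make the usage comparison (ITT, Evaluable and struggler versions) randomised group only, by an unequal-variance two-sample test at one-sided 0.025. This is the basis of 3.6, so the sample size stands.
2. Fit the adherence logistic model on randomised group alone.
3. Delete the 5% interaction pre-test.
4. Move myAir use and group-by-myAir to exploratory analyses, defining 'Yes' (measure, threshold, time window) and naming the contrast tested.
5. Allow a supportive myAir-adjusted model only if status before randomisation is available, and then as a main effect only.

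Items 1 to 4 are wording. The price is any precision myAir would have bought. At equal 50% uptake it explains b² × 0.25/2.5² of control-arm variance, which is 1% at b = 0.5 and 16% at b = 2.0. Power is then about 81% for group alone against about 81 to 89% with the factor in an unequal-variance calculation. Item 5 may need registration dates or a new baseline item, since 4.2 names none.

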1 INTRODUCTION

Obstructive Sleep Apnea (OSA) is a condition characterized by the partial or complete collapse of the upper airway during sleep. OSA comprises a continuous spectrum of severity ranging from simple snoring and upper airway resistance through mild to severe symptomatic obstructive hypopnea and apnea. The prevalence of sleep disordered breathing in the adult population is 24% males and 9% for females¹. The prevalence of symptomatic OSA in the adult population has been estimated to be 4% in males and 2% in females¹. These patients demonstrate behavioral and neuropsychological consequences to varying degrees, including excessive daytime sleepiness, intellectual deterioration and depression². More serious consequences include arterial systemic hypertension, arterial pulmonary hypertension and heart disease³.

The treatment of choice for OSA is Positive Airway Pressure (PAP). PAP acts as a positive airway splint, delivering a fixed positive airway pressure to the upper airway via a tube and mask. Humidification is used during PAP therapy to improve comfort of the delivered air and alleviate nasal dryness/congestion.

Although PAP therapy is the gold standard treatment for OSA, adherence to treatment is often poor. CMS guidelines define adherence as 4 or more hours per night of therapy use on 70% of nights during a consecutive 30-day window within the first 90 days of setup⁴. Anywhere from 30 to 85% of patients will be non-adherent according to this definition of adherence, which can be explained, in part, by factors such as socioeconomic status, age, gender, severity of presenting symptoms, health values/beliefs, and social support⁵. Importantly, patients who immediately adopt therapy, within the first 3 days, are significantly more likely to be adherent at 30 days⁶, and patients' usage at 1 month is significantly predictive of adherence at 1 year⁷. Without sustained, long-term therapy adherence, patients are at risk of negative health outcomes including but not limited to cardiovascular disease, stroke, diabetes, and depression. This study tests whether a combined financial plus social incentive can help users new become adherent to PAP therapy.

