3.2 STUDY DESIGN

This is a prospective, randomized, two-arm, open-label study to evaluate effectiveness of applying financial and social incentives via a smartphone-based app in helping participants achieve adherence to therapy. Randomization will include an allocation ratio of 2:1 (control:treatment).

Two 'site to participant' contacts are required during this study. These contacts can either occur at the clinical site or remotely (e.g., by telephone). During the initial contact, their interest in the study and eligibility will be confirmed, then they will be consented, asked to complete the Baseline Questionnaire, and their demographic information will be collected on case report forms (CRFs).

Participants randomized to the intervention (Group B) will be provided with information and assistance in downloading Restful to their smartphone and registering with Wellth.

At the final contact (90 days), the participant will be asked to complete an End of Study Questionnaire and the investigative staff will collect PAP therapy data for the trial period and record it on CRFs. Participants in Group B will have access to the Restful app discontinued. This completes the participant's active participation in the study.

Daily usage data from AirView will be collected and transmitted electronically from usage initiation to 90 days, and then through 180 days.

Study data will be captured on CRFs. See **Appendix A** for the **Baseline and End of Study Questionnaires**. See **Appendix B** for **Participant Instructions** related to the study procedures and the Restful app.

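### The primary usage model adjusts for no baseline characteristic, although the plan names prognostic factors and collects demographics before randomisation: a modest, avoidable loss of efficiency

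*Combined protocol and SAP*

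**What the plan says.** Section 3.9 compares mean usage at 90 days "using a two-way ANOVA on the ITT population". The terms are given in one sentence: "Randomization group and myAir usage (Yes/No) will be included as factors in the model". Their interaction stays only if it is significant at 5%. The struggler subgroup uses the same model, and the adherence logistic regression has the same two factors with their interaction. No covariate-adjusted version of the primary comparison is specified, even as a sensitivity analysis.

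Section 1 says that non-adherence under the CMS definition can be "explained, in part, by factors such as socioeconomic status, age, gender, severity of presenting symptoms, health values/beliefs, and social support".

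In section 4.2, step 2 of the enrolment contact enters device information and "demographic, and baseline data into the electronic data capture (EDC) system". Randomisation is step 3. The baseline questionnaires are listed beneath step 3, separately for each group. Section 3.2 also places the Baseline Questionnaire at the initial contact but does not say whether it precedes randomisation.

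Section 3.7 names baseline perceived disease severity, claustrophobia, coping skills and health literacy. Its change endpoints for ESS and FOSQ-10 imply baseline values of both.

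Section 3.9 uses baseline data for descriptive summaries, for between-group tests ("Baseline demographics and psychosocial factors for the control and intervention groups will be compared with t-tests and Fisher's exact tests, as appropriate") and for secondary moderator models of usage. myAir information comes from a report on "participants who registered for myAir and number of times they engaged with the app during the study".

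**The concern.** When a plan names characteristics that it believes drive the outcome and records some of them before randomisation, adjusting the primary comparison for them is usually worthwhile. Adjustment removes part of the residual variance, narrows the interval for the treatment effect and allows for chance imbalance between groups of 200 and 100. It needs no extra participants. Covariates chosen in advance raise no suspicion of selection; covariates added after results are seen do.

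The plan instead tests baseline differences between the groups. Under proper randomisation such tests examine a null hypothesis already known to be true, and they correct nothing if an imbalance appears.

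The one extra factor in the model, myAir usage, does not fill the gap. The app is optional (section 5.3) and its use is recorded during the study, so it is not a baseline characteristic.

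What is at stake is the width of the primary interval and some power, not the validity of the comparison.

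**Working it through.** **Inputs.** From section 3.6: SD 2.5 h (control) and 2.0 h (test), difference 0.8 h, one-sided alpha 0.025, 180/90 after dropout and 200/100 enrolled. The 0.8 h is described as 160% of the minimally clinically significant difference, which is therefore 0.8/1.6 = 0.5 h. The documents give no R2, so 2% to 20% is an assumed range.

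**Method.** Two-sample t-test with unequal variances, power from the noncentral t with Satterthwaite degrees of freedom. SE = sqrt(2.5²/n1 + 2.0²/n2). Baseline adjustment is approximated by multiplying both SDs by sqrt(1 − R2). The unadjusted participant number giving the same precision is N/(1 − R2).

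**The plan's own figure.**
- 180/90: SE = sqrt(0.03472 + 0.04444) = 0.281 h; power at 0.8 h is 80.8%.
- The smallest 2:1 design reaching 80% is 178 + 89 = 267 (80.4%), so the stated 270 reproduces.
- 270/0.9 = 300, as stated.
- 200/100: SE = sqrt(0.03125 + 0.04) = 0.267 h; power at 0.8 h is 84.7%. The 95% half-width is 1.970 × 0.267 = 0.53 h.

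The 200/100 row is the relevant one for the ITT analysis, because missing days count as zero usage and all 300 stay in.

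**With adjustment, at 200/100:**

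| Assumed R2 | SE (h) | 95% half-width (h) | Power at 0.8 h | Power at 0.5 h | Equivalent unadjusted N |
|---|---|---|---|---|---|
| 0 | 0.267 | 0.526 | 84.7% | 46% | 300 |
| 2% | 0.264 | 0.521 | 85.4% | 47% | 306 |
| 5% | 0.260 | 0.513 | 86.5% | 48% | 316 |
| 10% | 0.253 | 0.499 | 88.2% | 50% | 333 |
| 20% | 0.239 | 0.470 | 91.6% | 55% | 375 |

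At 180/90, power at 0.8 h goes from 80.8% to 81.6%, 82.8%, 84.7% and 88.6% over the same range. An R2 of 10% there gives SE = 0.281 × sqrt(0.9) = 0.267 h, the precision of 300 unadjusted participants. That is what the 10% dropout allowance buys.

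**Which covariates are safely available.** Setting sections 3.7, 3.9 and 4.2 side by side:
- Demographics are recorded at step 2, before randomisation at step 3. Age and gender qualify.
- Site is known at enrolment, but matters only if the second of the one or two planned sites opens.
- ESS and perceived disease severity are baseline measures, but section 4.2 lists the questionnaires after randomisation in an open-label trial. They qualify only if completed before the participant learns the allocation.
- Self-efficacy and social support appear in section 3.9 as factors that the intervention may affect. Nothing shown says that they are measured at baseline.

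**The case against.** The case against is substantial. An unadjusted randomised comparison is valid, and the plan meets its power target without covariates. The gain is assumed and may be small: at an R2 of 5% the half-width shrinks by about 0.013 h, under one minute, and at 2% power rises by less than one percentage point. Section 1 says only that the factors explain non-adherence in part, and it speaks of the binary CMS definition; carrying this over to mean hours is an inference. The order in section 4.2 may exclude the questionnaire scores, and age and gender alone may explain little. The calculation also starts from the two-sample test of section 3.6, not from the two-factor model, so the increment over the planned model is not known exactly.

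All of this stands. It limits the size of the point and the covariate list. It does not remove the point, because pre-randomisation demographics can be added at almost no cost even if they prove weak.

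A reader might infer three stronger things that the documents do not support:
- That the primary result is biased or the trial underpowered. Nothing shows bias. The 46% power at 0.5 h follows from the choice to power for 0.8 h, and adjustment lifts it only to 47–55%.
- That a large, known amount of precision is lost. No R2 is given.
- That the baseline data go unused. They are summarised, support the ESS and FOSQ-10 change endpoints and enter secondary moderator models of usage. They are absent only from the primary model and its struggler copy.

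**Conclusion.** The point holds as a recommendation to improve efficiency. The primary and struggler ANOVAs contain no baseline covariate, the plan itself names plausible prognostic factors, and at least age and gender can be used without doubt about timing. On the assumed R2 range of 2% to 20%, power for 0.8 h at 200/100 rises from 84.7% to between 85.4% and 91.6%. The lower part of that range is the safer expectation if only demographics qualify. The figures rest on the SDs in section 3.6, on an R2 that is the same in both arms, and on the approximation of scaling both SDs. The change is worth making because it is cheap, and it should be made before any outcome data by arm are examined.

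**What to change.** In section 3.9:

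1. Make the primary analysis a linear model of mean 90-day usage on randomised group plus a list fixed before any outcome data by arm are examined: age, gender, and site if two sites open. Use the same list in the struggler analysis.
2. Add baseline ESS and perceived disease severity only if they are completed before the allocation is disclosed. State the order of questionnaires and randomisation in section 4.2, and make it agree with section 3.2.
3. Impute a missing covariate with the overall mean so that every ITT participant stays in the model.
4. Do not treat myAir usage as baseline adjustment. It is recorded during the study and is not on the list above; a model that includes it can be shown as supplementary.
5. Present baseline characteristics by group descriptively and drop the t-tests and Fisher's exact tests.
6. Treat covariates in the adherence logistic model as optional. They change the odds ratio from a marginal to a conditional one, and its interval need not narrow. If they are added, say which odds ratio is reported.

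Cost: analysis wording and at most five model terms, against about 297 residual degrees of freedom (300 participants less three parameters). No new data are needed. If the questionnaires are now completed after allocation, including their scores would also require a change to the enrolment sequence.

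### Section 3.9 lets a 5% interaction test decide the primary model and does not say which group contrast is primary if the interaction is kept

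*Combined protocol and SAP*

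**What the plan says.** Section 3.9 compares mean PAP usage at 90 days "using a two-way ANOVA on the ITT population". "Randomization group and myAir usage (Yes/No) will be included as factors in the model", and the interaction of the two "will only be retained in the model if it is significant at the 5% level". The section names no coding, contrast or type of sums of squares for the case where the interaction is kept. It gives no significance level for the primary comparison and no adjustment for the selection step.

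The struggler subgroup is analysed "using a two-way ANOVA on the struggler population as described above", so it inherits the rule. The logistic model for adherence in the same section always contains the interaction, with no selection step.

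Section 2 asks whether the scheme increases usage. Section 3.6 sizes the trial on one overall difference: the sample size "is required to yield an 80% probability of detecting a difference of 0.8 hours in mean usage", "when the standard deviation is 2.5 and 2.0 in the Control and Test groups, respectively", and the calculation is "based on a one-sided, two sample t-test, using a significance level of 0.025".

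**The concern.** A primary analysis should estimate one quantity fixed in advance. Here only the trigger is fixed. If the interaction is dropped, the group term is the overall difference adjusted for myAir use, which is what Sections 2 and 3.6 ask about. If it is kept, the group term may be something else, and someone has to choose the contrast after the interaction result is known. Two competent analysts following Section 3.9 could report different primary estimates and different conclusions from the same data.

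**Working it through.** **1. The plan's own figure.** Inputs from Section 3.6: "with 2:1 randomization (180 in Control group, 90 in Test group"), SDs 2.5 and 2.0, difference 0.8 h, one-sided 0.025.

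SE = √(2.5²/180 + 2.0²/90) = √(0.0347 + 0.0444) = 0.281. Power ≈ Φ(0.8/0.281 − 1.96) = Φ(0.88) = 0.811; by noncentral t with Satterthwaite df it is 0.808. Then 270/0.9 = 300. The sample size is reproduced.

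**2. What the group term targets.** Let δN and δY be the effects in myAir non-users and users, and p the share of users, taken as equal in both arms.

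- Additive model: pδY + (1 − p)δN.
- Interaction kept, reference coding (non-users as reference): δN.
- Interaction kept, Type III: (δN + δY)/2.
- Interaction kept, Type II: the same contrast as the additive model, tested against the fuller model's residual.

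Fix the average effect at 0.8 h and let the effect be 1.0 h larger in users, so δN = 0.8 − p and δY = 1.8 − p:

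| p | δN | δY | Additive, Type II | Type III | Reference |
|---|---|---|---|---|---|
| 30% | 0.5 | 1.5 | 0.8 | 1.0 | 0.5 |
| 50% | 0.3 | 1.3 | 0.8 | 0.8 | 0.3 |
| 70% | 0.1 | 1.1 | 0.8 | 0.6 | 0.1 |

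If the effect is instead 1.0 h smaller in users, the reference target is 0.8 + p, that is 1.1, 1.3 and 1.5 h, and Type III targets 0.6, 0.8 and 1.0 h.

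**3. Power under the written rule.** Simulation at 200/100 with SDs 2.5/2.0 and myAir use independent of arm. The interaction is tested two-sided at 5%. The group term is read from whichever model results and tested one-sided at 0.025. That level is borrowed from Section 3.6. The myAir share and the interaction size are assumptions. Entries are for p = 30/50/70%.

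| | Effect 1.0 h larger in users | Effect 1.0 h smaller in users |
|---|---|---|
| Interaction kept | 34/40/34% | 34/40/34% |
| Additive, fixed in advance | 80/81/81% | 81/80/80% |
| Rule with Type II | 80/81/81% | 81/80/81% |
| Rule with Type III | 86/81/64% | 64/80/86% |
| Rule with reference coding | 56/49/53% | 87/88/87% |

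Independent runs agree within simulation error; across them reference coding gives 49-57% and 86-88%. With a uniform 0.8 h effect the interaction is kept in 3-4% of trials, and power under any coding is within about 1 point of the additive model.

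**4. Effect on the estimate.** Take 180/90, 70% users, 0 h in non-users and 1.143 h in users, so the average is 0.7 × 1.143 = 0.80 h. The interaction is kept in 39% of trials. In those trials the mean estimate is 0.45 h (Type III) or −0.42 h (reference coding); when it is dropped the mean is 0.80 h.

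**5. Type I error, no effect anywhere.** With SDs 2.5/2.0 at 180/90 the ANOVA pools the variance: (179 × 6.25 + 89 × 4)/268 = 5.50, SD 2.35. The pooled SE is 2.35 × √(1/180 + 1/90) = 0.303, against a true SE of 0.281, a ratio of 1.076. The one-sided error of the additive test is therefore 1 − Φ(1.96 × 1.076) = 0.017. Under the rule it is about 0.017-0.019 (Type III) or 0.020-0.024 (reference coding) for 30-70% users. With equal SDs and 20-80% users it is about 0.024-0.030 (Type III) or 0.027-0.037 (reference coding).

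**The case against.** **The rule itself is harmless under one standard reading.** This is correct. Type II sums of squares is an ordinary way to read a two-way ANOVA, and with it power stays at about 80% and type I error at its usual level. The harm comes from combining the retention rule with an unstated contrast. A reader might infer that testing the interaction first is a flaw under every reading; the text does not support that. Nor does it select Type II, so the gap remains.

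**Reference coding is a regression habit, not an ANOVA main effect.** Also fair. It gives the most extreme figures and is the least natural reading of Section 3.9. Type III is a natural reading, and it alone gives 64-86%.

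**The power effect runs both ways.** It does. A reader might infer that the rule costs power. With the opposite sign, reference coding raises power to 86-88%, and Type III can gain, lose or leave it unchanged. The point is that power depends on coding. The assumed 1.0 h interaction is also large beside the 0.8 h design effect, and nothing in the documents supports its size or sign.

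**Type I error is sound.** Under the plan's SDs it is. A reader might point to the minority of null trials that keep the interaction (about 3-5%), where the error can be well above 2.5% with reference coding. That is a conditional rate in few trials; the overall rate is what the design must control.

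**Strugglers are a subgroup.** Agreed. The argument about a single confirmatory quantity does not extend to them, and no size was computed for them. Aligning the model there is for consistency only.

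**Conclusion.** The point holds as a gap in the definition of the primary result. Section 3.9 lets the data choose the model and leaves the primary contrast undefined in one of the two outcomes, so the tested quantity can move away from the overall difference that Sections 2 and 3.6 address.

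The size is conditional. It is material if the effect differs by myAir use: with the assumed 1.0 h interaction, roughly a third or more of trials would reach the undefined branch, and the coding then largely decides the answer. It is negligible if the effect is uniform.

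A claim that the rule inflates the false-positive rate is not supported: overall one-sided error is at most about 2.5% with the protocol's SDs, and at worst about 3.7% with equal SDs and reference coding. These figures assume a 2.5% one-sided level and myAir use unrelated to arm. Whether myAir use is in fact unaffected by arm is a separate question, and settling it would not close this gap.

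**What to change.** In Section 3.9, replace the retention rule with a statement that the primary test is the group term from the ANOVA with group and myAir use and no interaction, whatever the interaction p-value. Use the same model in the struggler subgroup. Report the group-by-myAir interaction and the differences within myAir users and non-users, with confidence intervals, as supportive results.

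Keeping the rule and naming the Type II contrast would remove most of the harm, but fixing the additive model is simpler and leaves nothing to the software.

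The cost is about one sentence, with no new data or participants. The downside is that, if the effect differs by myAir use, the primary result reports only the average and the difference appears only among the supportive results.
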